2. are between 21 and 70 years of age
3. has difficulty with hand functions in activities of daily living (e.g., dressing, grooming, feeding)
4. has a stable medical condition without cardiopulmonary disease or frequent autonomic dysreflexia that would contraindicate participation in upper extremity rehabilitation or testing activities
5. are capable of performing simple cued motor tasks
6. has the ability to attend 2 to 5 weekly physical therapy sessions and testing activities
7. has adequate social support to be able to participate in weekly training and assessment sessions for the duration of 6 months within the study period.
8. has the ability to read and speak English

will be included in the study.

Exclusion criteria. Individuals who

1. has an autoimmune etiology of spinal cord dysfunction/injury
2. has a history of additional neurologic disease, such as stroke, MS, traumatic brain injury, etc.
3. has peripheral neuropathy (diabetic polyneuropathy, entrapment neuropathy, etc.)
4. has rheumatic diseases (such as rheumatoid arthritis and systemic lupus erythematosus)
5. has significant medical disease, including uncontrolled systemic hypertension with values above 170/100 mmHg; cardiac or pulmonary disease; chronic contagious disease, such as Hepatitis B and C, HIV; uncorrected coagulation abnormalities or need for therapeutic anticoagulation.
6. has active cancer
7. has cardiovascular or musculoskeletal disease or injury that would prevent full participation in the physical therapy intervention
8. unhealed fracture, contracture, pressure sore, urinary tract infection, or other illnesses that might interfere with upper extremity rehabilitation or testing activities
9. has any condition that would render the patient unable to safely cooperate with the study tests, as judged by the screening physician
10. are pregnant
11. has received botulinum toxin injections in the upper extremity muscles in the prior 6 months
12. has undergone tendon transfer or nerve transfer surgery in the upper extremity
13. are dependent on ventilation support
14. has an implanted stimulator (e.g., vagus nerve stimulator, pacemaker, cochlear implant, etc.).
15. has depression or anxiety based on Patient Health Questionnaire (PHQ-9) (score >9/27) and General Anxiety Disorder-7 item Questionnaire (score >9/21), respectively.
16. has alcohol and/or drug abuse.
17. has cognitive impairment based on the Short Portable Mental Status Questionnaire (SPMSQ) (score >2/10).

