After Phase I, patients will be randomized to receive either physical therapy alone (Arm A) or physical therapy plus transcutaneous spinal cord stimulation (Arm B) for 6 weeks. Then, patients will be followed up for an 8-week wash-out period, during which neither study intervention will be administered. During wash-out period, patients will not be allowed to receive treatments that violate exclusion criteria (e.g., botulinum toxin injections or tendon/nerve transfer

surgery in the upper extremity) or new treatments that could affect the study's outcome (e.g., alternative exercise therapies or robotic rehabilitation targeting upper extremity function).

However, they can continue to get their regular lower extremity physiotherapy.

Next, the intervention arms will be crossed over, i.e., patients who received the A intervention arm first will receive the B intervention arm, and vice versa, for another 6 weeks. In each intervention arm, sessions will last 2 hours/day, 2-5 days/week.

Transcutaneous Spinal Cord Stimulation Procedure: Transcutaneous spinal electrical stimulation is a non-invasive neurostimulation technique. Stimulation will be delivered through the skin using surface hydrogel electrodes, which are commonly used in practice today.

During the first stimulation session, optimal electrode placement and stimulation parameters will be determined using hand function testing and electromyographic (EMG) testing of the upper extremity muscles. Hand function will be tested by the abbreviated GRASSP test, Quantitative Prehension subscale, pinch and grip force measurements, and Capabilities of Upper Extremity Test (Cue-T). EMG testing will be done using skin surface recording electrodes.

Transcutaneous spinal stimulation paradigms that elicit appropriate muscle activation with the lowest threshold stimulation current will be identified. A painless cutaneous enabling motor control paradigm will be used for this purpose: biphasic or monophasic rectangular pulses of 1.0 ms per phase duration will be delivered at a frequency of approximately 30 times per second (Hz). Within these pulses, a very high carrier frequency of 10 kHz is delivered to avoid painful sensations as the current crosses the skin (i.e., the Russian Method of muscle stimulation). Stimulation intensity will range from 1 to 180 mA. During the initial testing, stimulation will be delivered for a duration of 10 to 30 seconds.

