Official Title of the study: ADDRESS: Activity Dependent Rehabilitation via Transcutaneous Electrical Spinal Stimulation to Restore Upper Extremity Functions in Spinal Cord Injury

NCT number: NCT03184792

Date of the document: February 22, 2022

Statistical Analysis Plan:

For comparison of the functional changes occurring during each intervention phase, one-way repeated measures ANOVA will be used with post-hoc pairwise analysis as per Tukey LSD test (IBM SPSS version 26). A Shapiro-Wilk Test will be used to determine whether repeated measurements follow a normal distribution. Mauchly's test will be used to analyze the assumption of sphericity, and degrees of freedom will be corrected using Greenhouse-Geisser estimates of sphericity when the assumption is violated. We will directly compare the benefits of training alone and stimulation combined with training by calculating the cumulative changes in each outcome measure across the two intervention arms. These values will be normalized to baseline to control for individual variation in function at the beginning of the study and compared between the training and stimulation + training interventions using a paired-samples T-test.

Additionally, score changes relative to the preceding treatment block will be calculated to compare the improvement rates between intervention phases repeated monthly. For all tests, $p < 0.05$ will be considered significant. All participants' data will be included in all analyses. Given the early stage of research and the lack of prior data on transcutaneous spinal cord stimulation for restoring upper limb function, power analysis and sample size calculations are not feasible.

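### If any required value is missing, the SAP's two named tests become complete-case analyses, which does not match a literal reading of its statement that everyone's data enter every analysis

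*SAP*

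**What the plan says.** The SAP is two paragraphs long and sets out three comparisons.

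- Change within each phase: "For comparison of the functional changes occurring during each intervention phase, one-way repeated measures ANOVA will be used". Mauchly's test is specified, and on violation "degrees of freedom will be corrected using Greenhouse-Geisser estimates of sphericity". This identifies the classical ANOVA rather than a mixed model.
- Training alone against stimulation plus training: baseline-normalised cumulative changes are "compared between the training and stimulation + training interventions using a paired-samples T-test".
- Rates of improvement: "score changes relative to the preceding treatment block will be calculated to compare the improvement rates between intervention phases". No test is named for this one.

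The second paragraph then says: "All participants' data will be included in all analyses". The SAP has no imputation rule, likelihood-based model or definition of who is analysed. The protocol has no rule for withdrawals, missed visits or patients who complete only one period.

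The nearest protocol text is in the inclusion criteria. A participant "has the ability to attend 2 to 5 weekly physical therapy sessions and testing activities" and "has adequate social support to be able to participate in weekly training and assessment sessions for the duration of 6 months". These concern who may enrol, not how an incomplete record is analysed.

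**The concern.** The crossover has two 6-week periods with a gap between them: "patients will be followed up for an 8-week wash-out period, during which neither study intervention will be administered". Measurements are two-weekly during the intervention, so a value can be lost at several points. A patient who leaves in period 1 or in the wash-out has no change for the second intervention and no place in the paired test. A patient who misses one entered visit is removed from the ANOVA, along with the visits that were observed.

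Two things are at stake. A complete-case result could be reported under a sentence saying that everyone was included. In addition, the ANOVA would discard observed visits that another method could use. No sample size is planned, so how much one lost patient matters cannot be judged from the documents.

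**Working it through.** The plan has no figure to reproduce: it gives no sample size, dropout rate or list of ANOVA levels. Every rate, size and correlation below is an assumption.

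**1. Mechanism.** Ten patients and four time points were simulated and one value removed. The software would not fit the repeated measures ANOVA until the whole patient was taken out. Error degrees of freedom then fell from (10−1)(4−1) = 27 to (9−1)(4−1) = 24. The paired t-test fell from 9 to 8 degrees of freedom. This was run in Python, not SPSS, but the loss of the whole patient follows from the structure of the test.

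**2. Information for the visit-level analysis.** Assume k = 4 levels, for example a starting value plus three two-weekly visits in a 6-week phase. Let q be the chance of a missed visit, with misses completely at random, equal correlation of 0.5 or 0.8 between visits, and known variances. For the last-versus-first contrast c, the information is 1/[c′(Σ p·Z′V⁻¹Z)⁻¹c]. The sum runs over missing-data patterns with probability p, Z selects the observed visits and V is their covariance. Results are relative to full data.

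| Missing pattern | q | Complete cases | All observed visits | Gain |
|---|---|---|---|---|
| Dropout, start value present | 2% | 0.98³ = 0.941 | 0.955-0.959 | 1-2% |
| | 5% | 0.95³ = 0.857 | 0.888-0.899 | 4-5% |
| | 10% | 0.90³ = 0.729 | 0.782-0.799 | 7-10% |
| Clustered (beta-binomial, intra-patient correlation 0.3) | 2% | 0.948 | 0.975-0.976 | 3% |
| | 5% | 0.873 | 0.937-0.940 | 7-8% |
| | 10% | 0.757 | 0.874-0.881 | 15-16% |
| Independent | 2% | 0.98⁴ = 0.922 | 0.974-0.975 | 6% |
| | 5% | 0.95⁴ = 0.815 | 0.935-0.938 | 15% |
| | 10% | 0.90⁴ = 0.656 | 0.870-0.876 | about 33% |

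The gain is the fourth column divided by the third, minus 1. Against simply using every patient with both the first and last value, the gain in the clustered and independent cases is only about 1%, 2-4% and 4-8%. Under dropout that comparison equals the complete-case one, because a patient seen last was seen throughout.

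A small-sample check used 10 patients, REML-estimated variances and 3000 draws. Variance ratios at q = 5% and 10% were 1.19 and 1.38-1.43 (independent) and 1.08-1.09 and 1.18-1.20 (clustered). Coverage of the 95% interval was 94.8-95.9%.

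**3. Direct treatment comparison.** Assume 8 patients with both periods and 2 with period 1 only, split equally by sequence, with no carryover and unit variance. With intervention and period terms and within-patient correlation ρ, each two-period patient contributes 1/[2(1−ρ)] to the information on the contrast. Each one-period patient contributes 1/4. The ratio to completers alone is therefore 1 + (2 × 1/4)/(8/[2(1−ρ)]) = 1 + (1−ρ)/8.

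- ρ = 0.2: 5.5/5 = 1.100
- ρ = 0.5: 8.5/8 = 1.063
- ρ = 0.8: 20.5/20 = 1.025

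With variances estimated by REML (8000 draws) the ratios were 1.080, 1.042 and 1.010.

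**4. Timeline against the 6-month criterion.** Up to 4 weeks of Phase I + 6 + 8 + 6 = up to 24 weeks to the end of period 2. Six months is about 26 weeks. Early follow-up ends at about 24 + 8 = 32 weeks, and a further visit comes at one year.

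**The case against.** The strongest reply is that nothing in the documents says data will be missing. Attendance is screened, and the 6-month criterion covers the planned course to the end of period 2. Sessions run 2-5 days a week, so a missed assessment might be made up. The later follow-up visits fall outside 6 months, but the SAP ties the ANOVA to the intervention phases and does not say that those visits enter it. All of this stands. It makes the point conditional, but it does not supply a rule for when a value is lost.

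The sentence can also be read as saying only that nobody is excluded by choice. On that reading there is no contradiction, but the SAP still does not say who enters each test.

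The size is open to challenge as well. For period 1 the starting value is taken in Phase I, before randomisation, and prehension and strength can be measured again there. If it is always present, independent misses leave 94%, 86% and 73% complete rather than 92%, 81% and 66%. The period 2 starting value, at the end of wash-out, can still be missed.

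Finally, a model with one value per intervention still omits a patient who leaves period 1 before its final assessment. That is correct, so the model alone cannot make the sentence literally true.

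A reader might infer that the third comparison also drops patients. It names no test, so that cannot be said of it.

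**Conclusion.** The point holds in conditional form and for the two named tests only. Once a required value is missing, those tests analyse complete cases, and no stated rule keeps the other patients. This is worth changing because a better method for the visit-level analysis costs little.

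The gain is modest under dropout, the most natural example here: about 1-2%, 4-5% and 7-10% at 2%, 5% and 10% per visit. It reaches about 33% only with 10% independent misses. For the direct treatment comparison it is about 1-8% with estimated variances, from an assumed 2 in 10 one-period patients, and near zero when within-patient correlation is high. There the need is mainly to state who is analysed.

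A reader might infer that the trial will lose a third of its information, or that its treatment estimate will be biased. The documents support neither: they give no missingness rate, sample size or reason for loss, so the size and direction of any effect are unknown. All figures rest on four assumed levels, equal correlation between visits and misses completely at random. Confidence is medium.

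**What to change.** 1. Replace the repeated measures ANOVA with a REML linear mixed model on all observed visits: visit as a fixed factor, a random patient intercept, and Kenward-Roger or Satterthwaite degrees of freedom. State the missing-at-random assumption. Pre-state one alternative covariance as a check, since a random intercept assumes equal correlation between visits.
2. For the direct comparison keep the SAP's outcome, the baseline-normalised cumulative change. Either retain the paired t-test, labelled as patients with both changes, or fit intervention and period as fixed effects and patient as random, so that patients with one completed period contribute.
3. Reword the sentence to say that no patient with observed data is excluded by choice. State that a patient with no end-of-period value contributes only to the visit-level model. Report the number of patients in each test.

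If the named tests stay primary, the minimum is to reword the sentence, define who enters each test and how one-period patients are handled, and report the numbers.

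The cost is SAP wording and slightly more modelling, with no extra data. The downsides are reliance on missing-at-random, which does not cover leaving because of an unobserved lack of benefit, and the need to keep the model simple in a small sample.
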